- Creation of study material e.g. ICF, study questionnaires, pre-screeners, digital protocol, and onboarding materials: 1-2 weeks*
- Enrollment of participants: 2-3 weeks
- Conducting the study: 2 weeks
- Data analysis & Report: 2 weeks

Execution plan

The investigators will carry out a within-subject comparative, open label study on enrolled participants. The experimental protocol is as follows:

Day 1: Start wearing the CGM sensor and let it self-calibrate for 24 hours

Day 2: Consume 1 serving of Test Meal for breakfast. Log the meal in the Tastermonial app.

Day 3: Consume 1 serving of Test Meal with GlucoTrojan for breakfast. Log the meal in the Tastermonial app.

Days 4-8: Participants will be instructed to take GlucoTrojan twice per day. Once during their typical breakfast meal and once during their typical dinner meal. Each breakfast and dinner will be logged in the Tastermonial app.

Days 9-13: Participants will continue with their typical lives but continue to log meals — breakfast and dinner — in the Tastermonial app.

Day 14: The experiment ends

On Day 1 and Day 2, testers must avoid eating foods or drinking anything except water after 10 PM and until 6 AM. At the start of each test, the investigators will ask testers to confirm that their blood glucose is within the typical resting range (70-100 mg/dL). If their blood glucose is not within the resting range, the investigators will ask testers to wait and check again in 15 minutes before starting the experiment. The test meal must be consumed within 10 minutes.

General instructions that apply from Day 1 to Day 14:

- 2 hours before the required action, refrain from strenuous exercise
- 2 hours after the required action, avoid other foods and refrain from strenuous exercise
- Use the proprietary Tastermonial smartphone app to scan the barcode or manually log test products and meals to record the serving size as they start eating. All events outside of the instructed ones should be noted in the food log.
- The context for each experiment should be consistent. E.g., if black coffee or tea is consumed within 2 hours after the required action, it should be consistently consumed for all experiments.

Data Handling & Analysis

Data Collection

The entire 14-day historical blood glucose data from the participants will be made available for analysis. The 2-hour postprandial blood sugar readings within a 15-minute interval will be analyzed, as well as the time-in-range of participants.

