Additional demographic profiles of participants will be collected and analyzed, including clinical parameters (age, sex, body weight, height, body mass index, meal composition; i.e.,calories, carbohydrates, fats, proteins, and fiber) and individual resting glucose range (Baseline Glucose Range) to determine their glycemic cohort.

The investigators will also collect qualitative data. Participants will be asked to report their feelings such as mood and well-being during and after the experiments in an online questionnaire. The questionnaire will be finalized with the approval of the company.

Data management

All documents relevant to the study, including completed ICFs, are hosted on a secure online portal. The ICFs are completed using a secured data transfer system on the HIPAA-compliant online portal. The company has access to the de-identified data set. The data is saved to a secured internal network. All data is anonymized during the analysis. HIPAA relevant PHI data privacy of participants is ensured on a secured online portal that uses the HIPAA compliant AWS servers. All participants are de-identified and labeled using a coding system.

Test Validation Methods

To ensure that the test was conducted under ideal conditions, e.g. on an empty stomach, the investigators rely on the participant's computed "baseline" or resting glucose average value, calculated as the average of all their glucose values from 1 AM to 4 AM each morning over the lifetime of the sensor. If the test was started far above the individual's **baseline range**, the test is considered an outlier and excluded from our initial analysis. This methodology was reviewed by a registered dietitian and a statistician.

The Baseline range

The baseline range of each individual is computed between 1 AM to 4 AM each morning over the lifetime of the sensor.

Several studies performed specifically using continuous glucose monitors suggest that a non-diabetic, healthy individual can expect:

- Maximum baseline range should not exceed 102 mg/dl for average non-diabetic testers
- ✤ Mean post-meal glucose peaks ranging from 99.2 ± 10.5 to 137.2 ± 21.1 mg/dl
- Time to post-meal glucose peak is around 46 minutes 1 hour
- Fasting glucose levels between 80-86 mg/dl

These are not standardized criteria or ranges but can serve as a simple guide for what has been observed as normal in individuals without diabetes.

iAUC Calculation

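### The stated fast ends at 6 AM, not at the test meal, so no rule bars intake before the test breakfast, and the safeguards reduce this gap without closing it

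*Protocol*

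**What the plan says.** All the rules on intake before the test meals stand in the protocol's Execution plan.

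- **Fast:** on Day 1 and Day 2, testers "must avoid eating foods or drinking anything except water after 10 PM and until 6 AM". These are the nights before the two test mornings.
- **Control test:** "Day 2: Consume 1 serving of Test Meal for breakfast". **Product test:** "Day 3: Consume 1 serving of Test Meal with GlucoTrojan for breakfast". Neither has a clock time.
- **Before the meal:** "2 hours before the required action, refrain from strenuous exercise". Food is not mentioned. The matching rule for the 2 hours after the meal covers both food and exercise.
- **Start check:** testers are asked to "confirm that their blood glucose is within the typical resting range (70-100 mg/dL"). If the reading is outside that range, they are asked to "wait and check again in 15 minutes before starting the experiment".
- **Other instructions:** events outside the instructed ones go in the food log, and the context of each experiment should be consistent.

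Test Validation Methods gives an empty stomach as an example of the ideal test condition. It infers this from glucose: a test started far above the tester's own 1-4 AM baseline range is treated as an outlier and left out of the initial analysis.

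**The concern.** The end of the fast is fixed by the clock, and the start of the test is not. A tester who drinks juice soon after 6 AM and takes the test meal at 8 AM breaks no rule that the protocol spells out, yet is not tested in the state the protocol wants.

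The main endpoint is a 2-hour increment, so glucose that is still rising or falling from earlier intake changes it. The standardised comparison has one test meal per condition (two portions are shipped), so intake on just one of the two mornings enters that tester's paired difference undiluted. Testing is at home and self-guided, which makes the written instruction the main control.

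**Working it through.** **Step 1. Which rules cover the time from 6 AM to the first bite?** The fast has ended. The 2-hours-before rule concerns exercise. The food rule starts after the meal. That leaves the start check, the baseline-range exclusion, the food log and the consistency instruction.

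**Step 2. What can pass the start check?** The Baseline range section gives a fasting guide of 80-86 mg/dL for people without diabetes. Against the upper limit of 100 mg/dL, the residual rise that still passes is 100 − 86 = 14 to 100 − 80 = 20 mg/dL. Very recent intake may not show at all, because the sensor lags by about 2-7 minutes and reports every 15 minutes.

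**Step 3. Effect on one test's iAUC (illustration).** The protocol has no figure to reproduce here.

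- From the protocol: 15-minute readings, a 2-hour window, the 70-100 mg/dL check, and a peak consistent with "Time to post-meal glucose peak is around 46 minutes 1 hour".
- Assumed: fasting glucose 85 mg/dL; peak at p = 50 min; test-meal rise 45 mg/dL; earlier intake with rise A = 10, 20 or 30 mg/dL, taken s minutes before; curve shape k = 2 or 3; no sensor lag; iAUC taken above the start reading.
- Response: r(t) = A·(t/p)^k·exp[k(1 − t/p)] for t > 0.
- Glucose: 85 + meal response at t + earlier response at t + s.
- iAUC: trapezoids above the reading at t = 0, from 0 to 120 min.

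Worked case (k = 2, A = 30, s = 120): t/p = 2.4, so the residual is 30 × 5.76 × exp(−2.8) = 10.5 and the start reading is 95.5, which passes. The iAUC is 2683 against 3555 with no earlier intake: 2683/3555 − 1 = −24.5%.

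| Minutes before | Rise A | Start reading, k = 2 / 3 | Check | iAUC change, k = 2 / 3 |
|---|---|---|---|---|
| 10 | 10 | 87.0 / 85.9 | pass | +16.1% / +19.2% |
| 10 | 30 | 90.9 / 87.6 | pass | +48.2% / +57.5% |
| 15 | 10 | 88.6 / 87.2 | pass | +10.4% / +14.0% |
| 15 | 30 | 95.9 / 91.6 | pass | +31.2% / +41.9% |
| 60 | 30 | 114.0 / 113.5 | fail | (caught) |
| 90 | 20 | 98.1 / 95.6 | pass | −28.8% / −30.5% |
| 90 | 30 | 104.6 / 100.9 | fail | (caught) |
| 120 | 10 | 88.5 / 87.1 | pass | −8.2% / −6.3% |
| 120 | 30 | 95.5 / 91.2 | pass | −24.5% / −18.8% |
| 150 | 30 | 89.9 / 87.0 | pass | −11.9% / −6.2% |
| 180 | 30 | 87.1 / 85.6 | pass | −5.3% / −1.8% |

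The sign changes because recent intake adds to the curve after the start, whereas older intake raises the start reading and then falls away.

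**Step 4. Sensitivity.** With fasting 86 mg/dL, peak at 46 or 60 min, a 7-minute lag, k = 3 and rises of 10 or 20 mg/dL, intake 5-15 minutes before passes and raises iAUC by about 20-47%. Intake 60-120 minutes before that passes lowers it by about 6-33%.

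**Step 5. From one test to the trial.** If a fraction f of testers has such intake before one condition only, and each affected test shifts by d, the mean for that condition shifts by about f × d. The documents give no value for f. If the fraction and the shift are the same in both conditions, the mean shifts cancel and only extra variance remains.

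**The case against.** The strongest reply is that the intended meaning is clear enough. A meal taken for breakfast is ordinarily the first intake of the day, 10 PM to 6 AM reads naturally as a minimum overnight fast, and the empty-stomach aim is stated. The step-by-step instructions that testers reach by QR code are not shown and may already say this. This stands to the extent that the food is only not barred. A reader might infer that the protocol permits eating before the test meal; it nowhere says so.

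The second reply is that safeguards exist, and they do catch cases: in the illustration, a 30 mg/dL rise 60 or 90 minutes before fails the check. The whole 14-day trace is annotated with the food log, so an excursion from intake well before the meal could be seen afterwards, and equal intake on both mornings would partly cancel. But a failed check leads only to a wait and a recheck, so a test can still start on falling glucose. Start readings in the low 90s are unlikely to count as far above baseline, no exclusion follows from the log, and the consistency instruction does not require fasting.

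The third reply is that the percentages depend on assumed curves. That is right. At 9:00 a 6 AM intake with a 30 mg/dL rise costs only 1.8-5.3%, and a 10 mg/dL rise costs 6.3-8.2% at 8:00. The protocol's limitations section also already concedes variance from non-strict conditions.

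**Conclusion.** The point holds as a badly fixed instruction: followed to the letter, the fasting rule does not secure the empty stomach that the protocol wants, and the safeguards only partly make up for it.

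For a single affected test that passes the start check, the illustrated distortion runs from a few percent or less up to about 30% lower (intake 90-180 minutes before), and about 10-58% higher (10-15 minutes before). This rests on the assumed curve shape, the assumed rises, and iAUC measured above the start reading. If the baseline were a fixed fasting value instead, residual glucose could only raise the iAUC. The 14-20 mg/dL margin applies to testers at the non-diabetic fasting guide.

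Two stronger readings are tempting. One is that earlier food always lowers the increment; the recent-intake cases show the opposite sign. The other is that the gap favours the product; nothing in the protocol ties earlier intake to one condition. What can be said is that intake on one morning adds noise to the paired difference, and bias if it differs by condition. With no frequency given, the effect on the trial mean is unknown.

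**What to change.** Reconcile the end of the fast with the empty-stomach aim:

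1. State that nothing except water is taken from 10 PM until the first bite of the test meal, on both test mornings, and carry the same wording into the instructions that testers see.
2. Have the tester confirm this in the app at the start of each test.
3. Flag any pair with logged intake between 6 AM and the test meal, and repeat the paired comparison without those pairs as a sensitivity analysis.

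The cost is one instruction sentence, one app item and possibly a few fewer pairs in the sensitivity analysis. The sample size does not change. In the model above, distortion from this source falls to zero when the rule is followed. The third step uses data already collected, but it finds only intake that was logged, so it does not replace the first two.

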Each participant's eating period (called a "meal") is normalized and overlaid in a data frame that captures glucose values over the course of the test. Several other metrics are computed, such as maximum and minimum values, standard deviation, and others. In particular, the investigators compute the iAUC ("incremental area under the curve"), a measure of the total amount of postprandial blood glucose level increased over the entire 2-hour period after eating. The methodology of iAUC calculation follows the gold standard used in the measurement of the glycemic index. The iAUC metric allows our team to easily compare and rank testing results, as well as compare against the pure sugar responses or the sugar tolerance test of an individual.

Data from each user is analyzed by our team and verified by a practitioner and a statistician. The raw Libreview data is annotated by the timestamps and the food log generated through the Tastermonial app.

Summary of obtained data

- A Glycemic Impact Exploratory Data Exports file in .xlsx/.csv format:
 - Anonymized blood glucose analysis including time-in-range
 - Per individual
 - Per experiment log
 - Metrics including iAUC, time to peak, peak (mg/dl), indicative GI & GL
 - Anonymized food log data
 - Anonymized tester profile and demographics data
 - Statistical Significance Analysis P-Value, Mean, Std Deviation at 95% confidence level

An example is shown below:

Limitations of the study and disclaimer

The investigators suggest the Company to not draw any final conclusion from the statistical analysis illustrated above, given the nature of this real-world observational study. A notable advantage of using this system is that volunteers are tested in real-world conditions. However, the test subjects were not under strict research testing conditions which could have caused a variance in the data generated. Further studies are required to further confirm our findings. As opposed to the randomized control trial studies, the collected data should provide a basis to further observe the different use cases, contexts and the customer profiles that the Company can market to.

Categorization of Study Risk and Dietary Supplement Safety

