The study falls under the "Minimal Risk" category, as the dietary supplement ingredients selected for the study have been well-tolerated in previous clinical studies and consumer products. These ingredients have either been on the market or submitted as new dietary ingredients to the FDA. The manufacturing process

used to obtain the extracts from the appropriate plant sources did not cause any chemical alterations. Moreover, the selected dietary supplements have a high safety profile, and the daily doses are within the upper limits tolerated by the FDA (where applicable). The ingredients are also on the GRAS list, and although there is a possibility that some participants may have a sensitivity to the herbal ingredients, there are no known side effects associated with the test product. The potential benefits of the dietary supplements outweigh the negligible risks, except for the potential risk of gastrointestinal upset for participants with previously unrecognized allergies or sensitivities to any ingredient. Regarding confidentiality, the risk is minimal as all study participant information will be de-identified, and since it is a virtual study, no confidential or protected information will be taken outside the standard. In the unlikely event that complications arise, and additional medical care is required, there is a slight financial risk to the participants.

Assessment of Benefits

This study aims to evaluate the benefits of using the test product, including enhancements in participants' quality of life and improvements in their blood glucose levels.

Conflict of interests

Ensuring the impartiality of this study, free from any actual or perceived external influence, is of utmost importance. To that end, any individual involved in the trial's design, implementation, analysis, publication, or any other aspect must disclose and appropriately manage any actual or perceived conflict of interest. In cases where a perceived conflict of interest exists, the individual must take measures to ensure their involvement in the trial is conducted appropriately.

Given that the sponsor will benefit financially from the study's success, it is imperative to manage their conflict of interest. To achieve this, an independent PI will oversee the study's execution, and Tastermonial will handle all aspects related to the design, administration of participant-focused materials, participant recruitment, and data collection.

Payment

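### Does the undefined margin for excluding tests that start far above baseline put the Day 2 versus Day 3 comparison at risk?

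*Protocol*

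**What the plan says.** Under Test Validation Methods, the protocol uses a personal resting value to judge whether a test began on an empty stomach. That value is "calculated as the average of all their glucose values from 1 AM to 4 AM each morning over the lifetime of the sensor". A test that starts far above the individual's baseline range is an outlier, "the test is considered an outlier and excluded from our initial analysis". The same section adds: "This methodology was reviewed by a registered dietitian and a statistician".

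The section on the baseline range repeats the 1 AM to 4 AM window but sets no lower or upper limit. It lists reference figures for people without diabetes, among them "Maximum baseline range should not exceed 102 mg/dl for average non-diabetic testers", and then says of them: "These are not standardized criteria or ranges".

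The Execution plan has a separate check before each test. Testers must "confirm that their blood glucose is within the typical resting range (70-100 mg/dL"), and otherwise wait 15 minutes and check again. This delays the meal and does not exclude data.

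The oversight named elsewhere is, in the iAUC section, "Data from each user is analyzed by our team and verified by a practitioner and a statistician" and, under Conflict of interests, that "an independent PI will oversee" the study's execution.

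**The concern.** An average is one number and a range needs two limits; the protocol moves between them without saying how. *Far above* has no unit, multiple or percentile. Neither the reference figures nor the 70-100 mg/dL check supplies the margin: the first are offered only as a guide, and the second is one range for everybody.

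The setting makes this look worse. The study is open label, and the calendar day reveals the condition. Glucose traces are annotated with the food log, and the company may ask for incoming results to be reviewed. Because the baseline averages nights over the whole life of the sensor, each person's final value exists only after both test meals are recorded. No named reviewer is said to be masked or to set the margin beforehand. Only two standardized meals are shipped, so one excluded test loses that participant's pair.

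The stake would be a Day 2 versus Day 3 result that depends on a cut chosen with the outcomes in view.

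**Working it through.** The protocol gives no margin, standard deviation or effect size here, so there is no stated figure to reproduce. The check asks two things: does a sensible choice of margin give a sound analysis, and how far could choosing the margin late distort it?

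**Inputs from the protocol.** 50 participants; one control and one product meal each; 70-100 mg/dL start check; 120-minute iAUC; 95% confidence level (taken as two-sided 5%).

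**Assumed inputs.** Start minus baseline is normal with mean 0 and SD 8 or 12 mg/dL. Personal baseline has mean 86 and SD 7 mg/dL. iAUC noise has SD 1000 mg·min/dL per test. iAUC changes by -30, -60 or -100 per mg/dL of start excess. There is no true product effect, and a paired t-test is run on complete pairs. The steepest slope is near the arithmetic ceiling: if the post-meal curve did not depend on the start at all, 1 mg/dL over 120 minutes would remove 1 × 120 = 120 mg·min/dL. Each setting had 10,000 runs, so Monte Carlo error is about ±0.4 points at 5%.

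**Step 1: one fixed cut.** With no cut, +25, +20, +15, +10 or +5 mg/dL, each used alone, the false-positive rate was 4.7-5.5% at SD 8 and 4.6-5.3% at SD 12. That is nominal within simulation error. The choice of number does not by itself bias the comparison.

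**Step 2: the most favourable of no cut, +25, +20 and +15.** Two-sided rate, nominal 5%, for slopes -30, -60, -100:

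| SD of start minus baseline | Start check followed | Start check ignored |
|---|---|---|
| 8 mg/dL | 5.4, 5.7, 6.2% | 6.3, 6.3, 6.8% |
| 12 mg/dL | 6.5, 6.3, 6.6% | 7.8, 8.9, 9.2% |

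A repeat of the simulation agreed within its error. With the check followed, the result is about 5.4% to 7%.

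**Step 3: pairs lost at +15.** Without the check, the share of tests dropped is 1 - Φ(15/SD):
- SD 8: 1 - Φ(1.875) = 3.0%, so 50 × 0.970² = 47.0 pairs remain.
- SD 12: 1 - Φ(1.25) = 10.6%, so 50 × 0.894² = 40.0 pairs remain.

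With the check, simulation gives 1.2% and 3.4% of tests dropped, leaving 48.9 and 46.8 pairs. The standard error grows by √(50/48.9) = 1.01 and √(50/46.8) = 1.03. Without the check the factors are √(50/47.0) = 1.03 and √(50/40.0) = 1.12.

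**Step 4: where larger figures come from.** Adding +10 and +5 to the menu raises the best-of rate to 9.2-10.8% (SD 8) and 10.1-13.4% (SD 12). A start 5 or 10 mg/dL above baseline is hard to describe as far above it.

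**The case for a change.** The strongest reply is that this is more than silence: the protocol writes an exclusion rule and leaves its operative term undefined, so two analysts could form different data sets. A second model, with cuts from 1 to 3 overnight SDs, gave 9.0-13.8% for a free choice of cut. If borderline pairs were dropped only when they disfavoured the product, false positives in its favour rose from 2.5% to between 5.7% and 46.0%. The company also wants to showcase the comparison, and writing down a margin costs little.

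The vagueness is real. The large figures carry less weight. The 9.0-13.8% range includes cuts as low as 1 SD, and that model has no start check. The selective-dropping case is not this rule: it excludes on the post-meal difference, whereas the protocol excludes on the starting value. The company's access is to incoming results; nothing gives it a say in exclusions.

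A further limit is that prediabetes and non-insulin-dependent diabetes are eligible. For participants whose resting glucose exceeds 100 mg/dL, the start check would not work as simulated. That weakens the with-check figures somewhat, and the no-check column of Step 2 bounds the effect under the same assumptions.

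**Conclusion.** No change to the plan is needed. The rule's purpose, data source, direction and consequence are stated; the missing pieces are a formula and a margin, which a protocol commonly leaves to an analysis plan that may exist but is not shown here. Any sensible single choice gives a valid comparison, because the rule uses a pre-meal value and treats both conditions alike. With the start check followed and cuts of +15 mg/dL or more, the worst discretionary choice adds about 0.4 to 2 points to a nominal 5% and costs about 1 to 3 of 50 pairs. All of this rests on assumed variability, not on trial data.

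The use made of the result also limits the stakes. The exclusion applies to an initial analysis, the output is described as an exploratory export, and the protocol advises the company against drawing final conclusions from the statistics.

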patented ingredient, "Reducose[®]", a natural water extract of novel White Mulberry Leaf that has been scientifically proven to reduce the absorption of sugars and other carbs by up to 40%. The effects have been confirmed previously via Randomized, Double-Blind, Controlled Trials (see Appendix I and II).

The Company is looking to conduct a real-world study of blood glucose responses to JBA GlucoTrojan (see specifications here) with a 5% concentration of Reducose[®]. The study will observe the real-world efficacy of GlucoTrojan when taken with high carbohydrate meals.

The Company wishes to use the collected data to showcase the comparative glycemic impact as well as testimonials from participants to build trust and loyalty with their customers.

Rationale

Reducing the health impact of dietary sugar intake is a public health priority. Mulberry leaf extract may reduce blood glucose responses following sugar intake by reducing gastrointestinal carbohydrate absorption via alpha-glucosidase inhibition activity of iminosugar constituents such as 1-deoxynojirimycin (DNJ). Mulberry leaf extracts are widely consumed in Asia for normalizing post-prandial blood glucose. Reducose has been tested in multiple clinical trials and lowers the postprandial glucose response by up to 40% (see Appendix).

Hypothesis

An appropriate dose of GlucoTrojan when co-administered with a complete meal will reduce the incremental area under the curve and the peak for plasma glucose concentration over 120 minutes in normoglycaemic adults when compared to the response to a control meal.

Study Objective

To compare the effect of consuming GlucoTrojan (mulberry-extract formula) with a meal (Test Meal) vs. having the meal alone (control) on the blood sugar response of 50 healthy (non-diabetes) adults, pre-diabetes or non-insulin dependent diabetes (Tester). Experiments will span 14 days.

Materials and Methods

Design

Testers will be given sachets of GlucoTrojan and standardized test meals. The experiment is conducted by logging foods on the Tastermonial app and syncing the continuous glucose data from the monitor into the

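### The hypothesised peak reads as an uncorrected sensor maximum, so a systematic additive Day 2 to Day 3 shift enters the peak contrast but cancels from iAUC

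*Protocol*

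**What the plan says.** The Protocol's Hypothesis section states that the product "will reduce the incremental area under the curve and the peak for plasma glucose concentration over 120 minutes", compared with a control meal. The word incremental is attached to the area and not to the peak.

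The iAUC Calculation section describes iAUC as an increase over the two hours after eating and then adds: "Several other metrics are computed, such as maximum and minimum values, standard deviation, and others". The Summary of obtained data lists "Metrics including iAUC, time to peak, peak (mg/dl), indicative GI & GL". Neither place defines peak or mentions subtracting a starting value. The Baseline range section uses the word for absolute levels: "Mean post-meal glucose peaks ranging from 99.2 ± 10.5 to 137.2 ± 21.1 mg/dl".

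One phrase could point the other way. Under iAUC Calculation each meal "is normalized and overlaid in a data frame that captures glucose values over the course of the test", and the protocol does not say whether this means aligning times or subtracting a baseline.

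Under Execution plan, the control meal is on Day 2 and the product meal on Day 3, once each and in that order for everyone. At the start of each test, testers are asked to "confirm that their blood glucose is within the typical resting range (70-100 mg/dL"), with a recheck after 15 minutes if they are outside it. Test Validation Methods excludes from the initial analysis a test begun well above the person's baseline range, which is computed from 1 AM to 4 AM readings over the life of the sensor.

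**The concern.** The product is meant to blunt the rise after a meal. A raw maximum contains that rise and also the level from which it began. If the group starts lower on Day 3, or the sensor reads lower that morning, the raw peak is lower with no help from the product. iAUC is protected against an additive shift as long as it is measured from the pre-meal reading. The two hypothesised outcomes could then disagree for a reason unrelated to the product, and the fixed order leaves nothing in the data to separate a shift from a product effect.

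The per-individual output raises a second problem. The export is broken down by individual, and the Timeline section offers marketing material built on single testers' comparative results. A single pair of meals has no averaging to remove a chance difference in starting value.

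**Working it through.** The protocol gives no SD, effect size or power calculation for its 50 testers, so there is no figure to reproduce. The checks below set the scale.

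**1. Size of the effect sought.** The protocol's benchmarks for people without diabetes are "Fasting glucose levels between 80-86 mg/dl" and mean peaks of 99.2 to 137.2 mg/dL. The rise is then between 99.2 - 86 = 13.2 and 137.2 - 80 = 57.2 mg/dL. Applying the maximum claimed reduction of 40% gives 0.4 × 13.2 = 5.3 to 0.4 × 57.2 = 22.9 mg/dL. This is for scale only: it combines the ends of separate ranges, and the 40% is claimed for the postprandial response in general.

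**2. Start gap allowed by the check.** 100 - 70 = 30 mg/dL within one person.

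**3. Random start differences, group mean.** Take an extreme assumption: starts uniform over 70-100 and independent between days.
- SD of one start = 30/√12 = 8.66 mg/dL.
- SD of the Day 3 minus Day 2 difference = 8.66 × √2 = 12.2 mg/dL.
- Contribution to the SE of the mean = 12.2/√50 = 1.7 mg/dL; 95% half-width 1.96 × 1.73 = 3.4 mg/dL.

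The mean is not biased and the false-positive rate stays at 5%.

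**4. Random start differences, one tester.** Under the same assumption, P(|difference| > 10) = (20/30)² = 44%. With an assumed within-person start SD of 4, 6 or 8 mg/dL, the SD of the difference is 5.7, 8.5 or 11.3 mg/dL. These are comparable with much of the 5.3-22.9 mg/dL range in step 1.

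**5. Systematic additive shift, group mean.** Simulated paired t-test: 50 testers, two-sided 5%, 20,000 runs, no product effect. Assumed: day-to-day SD of the rise 15 mg/dL per occasion; start SD 3, 5 or 8.66 mg/dL; shift carried fully into the peak. The entries are the share of studies with a significant result in the product's favour.

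| Day 3 minus Day 2 shift (mg/dL) | Absolute peak | Peak minus pre-meal value |
|---|---|---|
| 0 | 2.2-2.6% | 2.3-2.5% |
| -2 | 8.1-9.1% | 2.5% |
| -5 | 29-37% | 2.5% |
| -10 | 81-89% | 2.4-2.6% |

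Hand check for -5 with start SD 5: the SD of the difference is √(2 × (15² + 5²)) = 22.4, the SE is 22.4/√50 = 3.16, and 5/3.16 = 1.58. The chance of passing the critical value of 2.01 is then about Φ(1.58 - 2.01) = Φ(-0.43) = 33%, against 34% simulated. An upward shift would hide a benefit in the same way.

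**6. Incomplete carry-over.** Write the peak difference as effect + b·D + error, where D is the start difference. Absolute peak carries b·D; subtraction leaves -(1 - b)·D. A pure additive sensor offset has b = 1 and cancels. If b is below 1, subtraction over-corrects, and if b is below 0.5 it leaves more start-related variance than the absolute peak has, because (1 - b)² > b².

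**The case against.** A reader might infer that the protocol defines peak as absolute. It does not. The unit mg/dl fits a rise as well as a level, and the undefined normalization could mean baseline subtraction. What the text supports is that peak is undefined and reads as absolute. Adjustment for the pre-meal value might also stand in an analysis plan that is not shown. That is possible, but the protocol itself names and lists this hypothesised outcome, and nothing in it points to a correction.

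A reader might also infer that every start difference counts as product effect. Step 3 shows otherwise: random differences add noise to a 50-person mean. Only a systematic shift biases it, and the documents give neither evidence nor a size for one.

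There are also safeguards: the overnight fast before each test, 24 hours of sensor self-calibration, the start check with its recheck, and the exclusion of high starts. They limit the problem without closing it. The check still admits a 30 mg/dL gap. The exclusion has no number, ignores low starts and applies only to the initial analysis. A baseline averaged over the sensor's life cannot correct a change from Day 2 to Day 3.

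Finally, absolute peak is a legitimate measure, subtraction is not always better (step 6), iAUC is already incremental, and the protocol labels its export exploratory and advises against final conclusions. All of this stands. It limits the weight of the point and argues for allowing covariate adjustment, but it does not remove the gap.

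**Conclusion.** The point holds in limited form. As written, the plan most naturally compares one uncorrected maximum on Day 2 with one on Day 3 in a fixed order. An additive shift between those mornings passes into that contrast to the extent that it carries into the peak. It cancels from iAUC, provided iAUC is measured from the pre-meal reading, which its description implies but does not spell out. At an assumed shift of -5 mg/dL, the chance of a spurious significant benefit is roughly 29-37% rather than 2.5%; with no shift there is no inflation. The shift sizes, the 15 mg/dL SD and full carry-over are assumptions. For single testers, the allowed start gap of 30 mg/dL exceeds even the largest benchmark effect of 22.9 mg/dL, so individual peak comparisons are vulnerable even without a systematic shift.

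The documents do not support the stronger claims that peak is declared absolute or that ordinary start differences bias the group result.

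**What to change.** Make the hypothesised peak baseline-corrected in the Summary, the Hypothesis and the metrics list, using the same pre-meal sensor value as iAUC. Fix one of two forms in advance:

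- the 0-120 minute maximum minus the pre-meal value; or
- the Day 3 minus Day 2 difference in peak, regressed on the uncentred difference in pre-meal values, with the product effect read at a pre-meal difference of zero.

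Keep absolute peak as a descriptive column. Report the Day 2 and Day 3 pre-meal values side by side, for the group and for any individual result shown. State what normalization of a meal means and which reading is the iAUC baseline.

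The cost is a definition and a simple calculation on data already collected. Error in the single pre-meal reading enters the outcome in either form. Subtraction over-corrects where start differences carry only partly into the peak; covariate adjustment avoids imposing that, though noise in the reading flattens the estimated slope. Neither form removes the fixed-order confounding or a proportional sensor error, and the report should say so.
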